The Adult Care and Treatment Package includes the following services:(U. MoH, September 2014)

1. HIV counseling and testing
2. HIV prevention services
3. Nutritional Counseling and support
4. Opportunistic infection screening and management
5. Screening and management of non-communicable diseases
6. Diagnostics and laboratory monitoring
7. Sexual and reproductive health
8. Counseling and Psychosocial support
9. ARV preparation, initiation and monitoring
10. Adherence and retention into care
11. Palliative care
12. Mental health

[figure not shown]
[figure not shown]

Fig 5: Study Schema

The outcome variables include:

- ART adherence scores at 6 and 12 months, as assessed by HIV Care Card for those on SoC arm and Self- reported adherence to ART as depicted on the mHealth dash board.
- Viral load suppression at 6 and 12 months, as test results from blood collected at months 6 and 12 with time to viral suppression.
- Retention rates at 6 and 12 months with time to loss to follow-up
- Stigma scores at study start and end

Data Management Analysis Plan

Data collected on paper CRF will be entered using Research Electronic Data Capture software (REDCap) which is a safe, secure, HIPAA-compliant, web-based application and facilitates offline and online data entry. Data will be exported to STATA 14.0, for analysis. Data will then be backed up and archived in both soft and hard copy to avoid losses. The data collected will be stored securely under lock and key to maintain patient confidentiality.

Data regarding call details in the system will be extracted from CFL tool database, exported into Stata for analysis.

[figure not shown]
Visit dates will be extracted from database and proportions lost to follow-up drawn and time to loss to follow-up estimated. Viral load results will be extracted and time to viral suppression with survival analysis curves drawn for both arms.

Data from the MoH HIV card regarding the ART regimen and start dates will be transcribed to the data collection tool and later entered on the REDCap system.

General data analysis

Data will be analyzed at three levels, first at the univariate level, then at the bivariate level and lastly at the multivariate level. A consort diagram will be drawn to show the screening, enrolment, randomization, follow-up and analysis flow of the study.

Univariate Analysis

Descriptive analysis will be done for the factors that influence adherence, virological suppression, stigma and retention in care. In addition, the distribution of the independent variables will be done with categorical data summarized using frequencies and percentages. Numerical data will be summarized using means and standard deviations for normally distributed data, and median and inter-quartile range for data that is not normally distributed.

Bivariate Analysis

The relationship between independent variables (age, gender, ART duration, marital status, education status, occupation and religion) and adherence and virological suppression will be analyzed using bivariate analysis made using cross tabular analysis and associations investigated using the Pearson Chi-square test.

The Chi-square test is based on the computational formulae below:

$$\chi^2 = \sum_{i=1}^r \sum_{j=1}^c \frac{(O_{ij} - E_{ij})^2}{E_{ij}}$$

Where

r is the number of categories of the ith explanatory variable

c is the number of categories of the dependent variable

[figure not shown]
O_{ij} is the observed number of observations in the ith explanatory

and jth dependent variable

E_{ij} is the expected number of observations in the ith explanatory?

and jth dependent variable

Further, odds ratios shall be used to analyze the relationship between the dependent variable and the independent variables. Variables found to be significant at p value of p ≤ 0.05 will be considered for the multivariable analysis.

Multivariate Analysis

Multivariable logistic regression will be used to determine the factors that influence adherence or virological suppression and retention in care. Variables found to be statistically significant at $p \leq 0.05$ in bivariate analysis and those considered to have a scientific explanation will be entered into the multivariable model.

The multivariate logistic regression adopted is based on the formulae below:

$$\ln \left[\frac{p_i}{1 - p_i} \right] = \beta_0 + \beta_1 X_1 + \dots + \beta_n X_n$$

[figure not shown]
Where;

X = independent variables

p_i = Probability of being adherent and virally suppressed

$1 - p_i$ = Probability of non-adherence or not suppressed virologically

β_0 = constant ; β_i = coefficient of the determinant

The study findings will be reported as odds ratios, confidence interval and independent variables found to have p value ≤ 0.05 at 95% confidence interval will be considered to be statistically significant in the final model.

[figure not shown]
After the final model, significant factors for ART adherence/ viral suppression will be computed.

Data Monitoring Committee:

The DMC will consist of 3 independent members with expertise in relevant clinical specialties, their responsibility is to ensure that the safety of study subjects is protected while the scientific goals of the study are being met. The previous CFL-RCT at IDI, had no major safety issues and neither were there any gender-based violence, so the DMC will suffice and will be involved in:

- Review the research protocol and plan for data safety and monitoring.

- Evaluate the progress of the trial, including periodic assessments of data quality and timeliness, participant recruitment, accrual and retention, participant risk versus benefit, performance of the trial site, and other factors that can affect study outcome.
- Make recommendations to the PI about continuation, termination, or other modifications of the trial based on the observed beneficial or adverse effects of the intervention under study.
- If appropriate, conduct interim analysis of efficacy in accordance
- Recommend solutions to address problems with study conduct, enrolment, and sample size and/or data collection.

Study visits (scheduled and unscheduled visit codes)

The total duration of the study is 18 months; follow up period is up to 12 months. The participant has a baseline visit (00.0) and is followed up at month 6 (168 days \pm 14 days) visit code 01.0, last visit is at month 12 (336 days \pm 14 days) visit code 02.0.

The participant might return at the clinic due to an illness, or repeat blood draw, this interim visit codes will be numbered sequentially from the previous scheduled visit. (00.01, 00.02 if its next to the baseline, if next to second visit, the code will be 01.01, 01.02 etc., if its next to last visit it will be coded 02.1, 02.2, etc.).

The study visit window is 2 weeks (14 days), beyond this period a visit code denoting an interim visit is given; e.g. Visit code 01.1 first contact with patient past visit 01.0 and 01.2 denotes second contact with patient past visit 01.0.

During enrolment, it is important to obtain the names and contact information for several individuals closely related to the participant (e.g., next of kin, friends, etc.). Such individuals can be contacted in the event that a participant does not return for follow-up visits. Physical contact tracing will happen if the patient takes 2 weeks past the scheduled visit.

Missed visit:

When the appointment is not honoured and the 14-day window passes, this is a missed visit. If a participant misses a visit (Visit window inclusive) a missed visit form is completed documenting the reason for missing (if known) and the attempts made to contact the participant, through mobile

phone or physical tracing. Several attempts to contact the participants must be made to ensure good retention. The attempts may include: Checking the General clinic schedule to sync the appointment visit, Calling the participant; Calling a relative who was disclosed to, or Visiting the participant's home: To minimise missed visits, through the web-interface on CFLU system, any dropped calls monitored on the dashboard, will trigger active follow-up and tracing of the participants.

Loss to follow-up:

If a participant misses 2 consecutive visits and unable to ascertain the vital status, this patient will be declared lost to follow-up, alternatively, if 3 months consecutively elapse, without acknowledging the patient's status, the patient will be labelled lost to follow-up. If a participant's whereabouts are not known for 3 months and the contact tracing is uneventful after 3 documented attempts, this participant is deemed lost to follow-up and a withdraw form is completed. In case the participant re-surfaces to the clinic when the study is still active/ongoing, the withdraw form is cancelled out and patient re-joins the study and a study visit is conducted.

Study Objective 3:

To evaluate the cost of mHealth in comparison to Standard of Care

Study design: Cost evaluation analysis

Study Purpose: To assess cost of mHealth intervention in comparison to standard of care

[figure not shown]
Primary outcome measure: Costs spent on the intervention participants in comparison to standard of care participants

A cost analysis of the intervention from a governmental perspective will be performed. The principle of marginal costing will be used to cost the resources utilised in the alternative strategies. All costs of a historical nature, the sunk costs such as resources invested in buildings, equipment, and vehicles will be ignored. Only costs related to the future, from the onset of the study, will be recorded.

[figure not shown]
Sources of cost information: The following costs will be assessed and classified under direct or indirect cost: Sources of cost data will be; program/ project documents, financial records.

Capital costs:

I. System Costs:

- Software monthly hosting (internet, cloud hosting, call bills,)
- Support maintenance
- Hard ware
 - Computers
 - Internet modem

Recurrent costs:

- I. Supplies (blood collection tubes, vacutainer holders, needle, cotton swabs)
- II. Transport to fro (clinic visit):
- III. Staff/ personnel salaries:

Induced costs:

- I. Transport costs
- II. Number of sick visits attended outside the clinic costs/fees incurred
- III. Airtime fees

Health outcomes:

The number of patients with viral suppression (<1000 copies) will listed per study arm at month 6 and 12, and these will be compared across arms.

Analysis:

Primary outcome measure will be Cost for mHealth Intervention.

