Secondly, the mHealth tool has been used previously for health promotion where it improved knowledge in sexual reproductive health and facilitated behavior change (Ippoliti & L'Engle, 2017). The IMB model posits that provision of information and motivation influences behaviours. We hypothesize that the CFLU tool will address existing knowledge gaps among YLWH through provision of health messages about HIV, ART and medication adherence. Daily pill reminders and visit reminders will motivate youth and will help to address forgetfulness and busy schedules, factors which were the main causes of medication non-adherence and missed visits in the Call for Life study. Addressing these factors will influence adherence behaviours.

Prior work suggests that patients with higher HIV knowledge are twice as likely to keep their appointments as those who are less knowledgeable. Knowledge of HIV coupled with a good client-provider was associated with increased CD4 count and a five-fold likelihood of achieving undetectable VL (Jones, Cook, Rodriguez, & Waldrop-Valverde, 2013). Lack of knowledge of correct dosing and time to take drugs was associated with non-adherence in those starting ART (Miller et al., 2003). HIV knowledge has also been shown to be associated with improved quality of life (Swindells et al., 1999).

Lastly, evaluation of the effect mHealth tool will include assessment of stigma scores at baseline and follow-up, HIV knowledge at baseline and follow-up, and adherence as measured by clinic attendance (visit adherence), phone interaction and viral suppression.

The IMB model was chosen because the intervention will provide information through health tip messages and motivation through daily calls. According to prior recipients of the CFLU mHealth intervention, voice calls and voice tones encouraged and motivated them to continue taking medication, which impacted their behaviours including honoring clinic visit appointments, taking medication on time and willingness to report any symptoms they may have had. These factors may have improved clinic attendance, ART adherence and viral suppression. This model is a better fit for the CFLU mHealth tool than similar behavior models e.g. the Capability-Opportunity-Motivation-Behavioral (COM-B) model.

[figure not shown]
CHAPTER TWO: LITERATURE REVIEW

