To assess effect of mHealth tool (CFLU) on ART adherence and knowledge of COVID-19 among YLWH naïve, initiating ART or on ART since Jun 2019.

RESEARCH & ETHICS COMMITTEE
[name]

Study design: Randomized control trial with 2 arms (Standard of Care or CFLU with Standard of Care)

Study purpose: To assess effect of CFLU on ART adherence among youth measured by interactive voice response to daily adherence calls mapped in the database and proportion with viral suppression of copies below 1000 copies/mL.

The intervention (CFLU) uses IVR calls or text messages delivered via MOTECH™ based Connect for Life technology™. The calls are delivered in 3 languages (Luganda, English and Runyakitara) and the participant has to make a choice of the preferred language during registration to the system. The system offers adherence pill reminders, health message tips, visit appointment reminders and receipt of self-reported symptoms.

A poor understanding of the disease among youths can result in delayed identification and treatment leading to rapid spread of infections among the community.

Study setting: Kiryandongo District, 3 sites offering HIV-ART. Kiryandongo hospital, Panyandoli Health Centre III and Nyakadote Health Centre II have been chosen as the study sites, the hospital has 1,322 YLWH and a viral suppression rate of 79% (Table 1). In 2018, a total of 637 YLWH were enrolled in care. By Jun 2019 and additional 218 YLWH had been enrolled in care. The current total at the site for age between 15-24 is 1,322. Overall retention was 79%. We have included the lower level health facilities since ART delivery is done majorly in these grassroot levels.

Study Population: Inclusion: YLWH (15-24 years), ART naïve or initiating ART since Jun 2019.

Exclusion: Hearing loss, severe illness likely to shorten life span, boarding school YLWH, Inability to use a basic mobile phone.

Sample size calculation:

Sample Size: X-Sectional, Cohort, & Randomized Clinical Trials (Kelsey et al., Methods in Observational Epidemiology 2nd Edition, Table 12-15; Fleiss, Statistical Methods for Rates and Proportions, formulas 3.18 & 3.19)

The sample size formula for the method described in Kelsey et. al. is:

$$n_1 = \frac{(Z_{\alpha/2} + Z_{1-\beta})^2 \bar{p} \bar{q} (r+1)}{r(p_1 - p_2)^2}$$

[figure not shown]
and

$$n_2 = rn_1$$

where

n_1 = number of cases in the intervention

n_2 = number of controls

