Ratio of sample size. Unexposed/Exposed:	1
Percent of Unexposed with Outcome:	79
Percent of Exposed with Outcome:	94
Odds Ratio:	4.2
Risk/Prevalence Ratio:	1.2
Risk/Prevalence difference:	15

	Kelsey	Fleiss	Fleiss with CC
Sample Size - Exposed	81	80	93
Sample Size-Noneexposed	81	80	93
Total sample size:	162	160	186

References

Kelsey et al., Methods in Observational Epidemiology 2nd Edition, Table 12-15
 Fleiss, Statistical Methods for Rates and Proportions, formulas 3.18 & 3.19
 CC = continuity correction
 Results are rounded up to the nearest integer.
 Print from the browser menu or select, copy, and paste to other programs.

Results from OpenEpi, Version 3, open source calculator--SSCohort
 Print from the browser with ctrl-P
 or select text to copy and paste to other programs.

MAKERERE UNIVERSITY
 SCHOOL OF MEDICINE
 RENEWAL
 VALID UNTIL

★ 10 FEB 2023 ★

RESEARCH & ETHICS COMMITTEE
 103 FOR EACH ARM, KAMPALA

Factoring 10% loss to follow-up, the total sample size will be 206(103 for each arm, KAMPALA)

[figure not shown]
Data collection procedures:

The intervention is mobile phone based IVR. However, the CLFU trial found that, it was observed that a good number of participants (50 of 256) at the urban site were not enrolled due to absence of a basic mobile phone, or had malfunctioning phone keyboards (for Poster Exhibition at the 20th International Conference on AIDS and STIs in Africa (ICASA 2019). Therefore, we shall provide a basic mobile phone to everyone in the study (SoC and intervention arm). To avoid stigma associated with a particular phone, we shall get 4 or more types of basic phones. Issues regarding simcard registration will be dealt with by the individuals.

Four study questionnaires will be administered at baseline and 6-monthly until the 12-month exit visit.

The questionnaires will capture:

- Sociodemographic and medical history
- Stigma scores
- Knowledge assessment
- Sexual behavior assessment
- Knowledge of COVID-19 (only at baseline)

The data will be entered using REDCap. Blood for viral load will be collected at baseline and at the 6 and 12-month visit.

Intervention: mHealth CFLU tool

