The tool capitalises on a basic mobile phone's core utilities of voice and short messaging services. The system design, development, testing and evaluation was done by Janssen and the Grameen Foundation (<http://motechsuite.org/index.php/implementations>). In 2015, Janssen Global Public Health Research and Development, in close collaboration with the Infectious Diseases Institute Kampala (IDI), developed Call for Life Uganda (CFLU) tailored to the needs of PLHIV in Uganda. The CFLU system follows the Health Insurance Portability and Accountability Act (HIPAA) Privacy and Security rules. While the Privacy rules deals with electronic Protected Health Information, the security rule covers administrative, physical and technical safeguards to ensure confidentiality, integrity and security of electronic protected health information. Data transaction between patient and system is encrypted when it comes to human subjects. The system is password protected, and interaction of system and patient is personalised with a secret code. The system interacts with the patient through a basic mobile phone via a keypad and with the health worker through a web-based interface. The system has options to either use interactive voice response or short message service and the user has to make a choice, get a secret pin code which ensures privacy to enduser.

Screening-Enrolment procedures:

All potential participants will be written on the screening log, and a screening form completed, reasons for screen failure will be documented on the screening log. Following successful screening, the participant will be referred to the Research Assistant (RA) to receive a

thorough explanation of the study so and informed consent is obtained. The RA then administers the stigma questionnaire along with the sociodemographic and medical information, , HIV knowledge and sexual behaviour questionnaires. A client locator form will be completed which will help in physical contact tracing, and the participant will be registered on the enrolment log.

Randomisation will follow (see details of randomisation procedure below) thereafter and the result in the sealed envelope will dictate whether the patient will be registered onto the Call for Life System for the intervention or continue with standard of care as per MoH HIV Management guidelines.

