2. TB TREATMENT HISTORY				
Anti TB regimen	Start date	End date	Change /Stop reason (Toxicity/ completed/ side effects)	TB treatment center
3. How often have you missed your ARV medication for the following reasons(since past visit: on follow-up) Tick all that apply				
Reason	Never	Rarely	Sometimes	Often
Away from home				
Simply forgot				
Had too many pills to take				
Wanted to avoid side-effects				

Did not want people to notice you taking them				
Felt sick, depressed or overwhelmed				
Ran out of drugs				
Felt healthy				
Had a change in daily routine				

Section G: Current Clinical Status/Therapy				
1. Current medications  Cotrimoxazole  Corticosteroids  Antibiotics _____  Other _____		 Antidiabetics  Anti Hypertension  Chemotherapy  Oral/injectable contraception 
 MAKERERE UNIVERSITY SCHOOL OF MEDICINE RENEWAL VALID UNTIL ★ 10 FEB 2023 ★ RESEARCH & ETHICS COMMITTEE [name] 
		
2. In the last weeks have you taken herbal or traditional medications?		2-a. If yes to # 2, why? Increase strength,  Yes  No Increase appetite,  Yes  No Make more blood (hematinic)  Yes  No Increase immunity  Yes  No Other _____  Yes  No		

[figure not shown]
Section H. Laboratory tests				
Viral load	 Yes		 No	
Blood storage	 Yes		 No	
DBS	 Yes		 No	

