- Days ago
- Weeks ago
- Months ago
- Years ago
- Never

13. If months or years ago, what is the most common reasons which prevented you from having sexual intercourse?

- No partner
- My health status
- Health status of my partner
- Am abstaining
- Other (specify)-----

14. The last time you had intercourse did you use a condom?

- Yes
- No
- Do not remember

15. The last time you had intercourse had you been drinking alcohol or marijuana in the few hours before?

- Yes
- No
- Do not Know

16. How many times in the last 2 months have you had sex without a condom?

- None

1-3
 3-10
 >10

17. Do you regularly use condoms?

Yes
 No

18. In the last 3 months, have you had any abnormal discharge/ ulcer/wound in your genito-urinary part?

Yes No (skip to 20)

19. If Yes, did you receive treatment

Yes, went to health worker
 Yes, I self-medicated
 No, I did not

20. Have you ever had forced or coerced sex?

[figure not shown]
Yes
 No (if no end here)

21. If yes to Qn 20 above, did you inform any one?

Yes
 No

22. If yes to Qn 21 above, whom did you inform?

Police
 Friend
 Relative (Specify relationship eg, Mum, sister, aunt)

Study Staff Name / Initials	Signature	Date
  		____ / ____ / ____ DD/MM/YYYY

xi. COVID-19 KNOWLEDGE ASSESSMENT AMONG YOUTH (BASELINE ONLY)

Section A: Patient Information							
1. Clinic number#	2. STUDY Number :			3. Date of Visit _____ / _____ / _____			
Have you ever heard or know about Corona Virus disease 2019? Yes  No  (if no stop)	Family/ friends 	Radio 	Newspaper 	Social media 	Internet 	Religious leader 	Medical personnel 
Where do you get your knowledge about Coronavirus?							

Questions developed using information from WHO <https://www.who.int/news-room/q-a-detail/q-a-coronaviruses>

Section B. Do you know any Symptoms of COVID-19								
Symptoms	Yes	No	Days	Symptoms	Yes	No	Days	
Fever				Aches and pains				
Dry cough				Nasal congestion/runny nose				
Sneezing				Sore throat				
Loss of smell				Loss of taste				
Shortness of breath				Diarrhea				
Have you had any symptoms above? List symptoms and action taken								

Section C. Knowledge about PROTECTION				Section D. Practices about PROTECTION (last 7 days)			

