Being able to hold your breath for 10 seconds or more without coughing or feeling discomfort means you are free from the coronavirus disease (COVID-19) or any other lung disease.						
Drinking alcohol protects you against COVID-19 and can be dangerous						
COVID-19 virus cannot be transmitted in areas with hot and humid climates						
Taking a hot bath prevents the new coronavirus disease						
The new coronavirus is transmitted through mosquito bites.						
Hand dryers effectively kill the new coronavirus?						
Spraying alcohol or chlorine all over your body kills the new coronavirus						
Eating garlic prevents infection with the new coronavirus						
The new coronavirus affects older people, and younger people are not susceptible						
Antibiotics are effective in preventing and treating the new coronavirus						
Chloroquine is effective in preventing and treating the new coronavirus						

Section F. HIV care

[figure not shown]
ART medications

Do you have antiretroviral drugs with you at the moment? Yes No

Are you taking your ART?

Yes No

Rate your adherence in the last month _____

Analogue visual scale 0-100

HIV care

Access to HIV services Walking Public transport (Matatu) boda boda Private vehicle

Do you have any concerns about your own health? Yes No

Do you think HIV infection increases the risk of acquiring COVID-19? Yes No

Has your HIV care been affected by any of the following?

Drug stock out No public transport Halt of private vehicles Fear of acquiring HIV at the clinic

Sickness of health care workers Unavailability of HIV services due to the response to COVID-19

Do you think your HIV care will be affected by any of the following?

[figure not shown]
Drug stock out No public transport Halt of private vehicles Fear of acquiring HIV at the clinic

Sickness of health care workers Unavailability of HIV services due to the response to COVID-19

Other medication

Were you prescribed drugs for any of the following?

- Diabetes
- Hypertension
- Anticonvulsants
- Contraceptives
- Anti TB drugs

Are currently taking them?

- Yes No

Are you taking any herb to prevent COVID-19/boost your immunity?

Yes _____ No

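### The month 6 and 12 adherence score is taken from a different source in each arm, so a between-arm difference in it cannot be attributed to the CFLU tool

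*Combined protocol and SAP*

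**What the plan says.** The first outcome listed under Study Objective 2 in section 3.4 is an ART adherence score for the month 6 and month 12 visits. Its source is given thus: "as assessed by HIV Care Card for those on SoC arm and Self- reported adherence to ART as depicted on the mHealth dash board". The second clause names no arm, but the screening and enrolment procedures settle it: "the result in the sealed envelope will dictate whether the patient will be registered onto the Call for Life System for the intervention"; everyone else continues on standard of care. Section 3.5 likewise describes registration only for those randomised to the intervention.

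The study purpose for Objective 2 describes adherence as "measured by interactive voice response to daily adherence calls mapped in the database and proportion with viral suppression". The theoretical framework (section 1.6) speaks of "adherence as measured by clinic attendance (visit adherence), phone interaction and viral suppression". Answering the system's calls is therefore counted as adherence, and only one arm receives those calls.

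Two adherence items sit on forms common to both arms:

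- The medical evaluation form (Appendix viii, Section F, item 3) asks "How often have you missed your ARV medication for the following reasons(since past visit: on follow-up". Section 3.4 says of the questionnaires: "Four study questionnaires will be administered at baseline and 6-monthly until the 12-month exit visit". This item is not named as the adherence score and has no scoring rule.
- A 0–100 scale headed "Rate your adherence in the last month" appears in Section F of Appendix xi. That form is titled "COVID-19 KNOWLEDGE ASSESSMENT AMONG YOUTH (BASELINE ONLY"), so the rating is not available at month 6 or 12.

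The Data Management Analysis Plan lists only ART regimen and start dates for transcription from the Ministry of Health HIV card. The study limitations in section 3.6 concede that call responses are taken as accurate self-report. They do not mention that the arms are measured differently.

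**The concern.** A randomised comparison needs the outcome to be measured in the same way in both arms. Here one arm is read from a clinic record and the other from replies to the intervention's own automated calls. If the two sources read differently for the same behaviour, that gap is added to or subtracted from the treatment effect. If they happen to cancel a real effect, the tool looks useless.

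Effect on ART adherence at months 6 and 12 is specific objective III (section 1.3.2), and no primary outcome is named for the randomised trial. As written, this score could be reported as the main answer to that objective.

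The legend to the logistic formula (Multivariate Analysis) defines the modelled probability as that of being adherent and suppressed together. The prose above it says adherence or suppression. If the legend were followed literally, the arm-specific score would also enter the suppression outcome.

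**Working it through.** **1. Is there any overlap of instruments between arms?** Setting the provisions side by side:

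| Source | SoC, months 6/12 | CFLU, months 6/12 |
|---|---|---|
| HIV Care Card adherence | designated score | not specified |
| Dashboard / IVR self-report | impossible (not registered) | designated score |
| Missed-dose item, Appendix viii | collected, not designated, unscored | collected, not designated, unscored |
| 0–100 rating, Appendix xi | baseline only | baseline only |
| Viral load | same blood test | same blood test |

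For the designated score there is no overlap. No bridging sample or calibration is planned, and no rule is given for scoring an unanswered call.

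**2. Can a model separate the two effects?** Take score = β₀ + β₁·arm + β₂·instrument for 103 + 103 participants. Arm and instrument are both 0 throughout SoC and both 1 throughout CFLU, so the two columns are identical. The design matrix has rank 2 with 3 columns. Only β₁ + β₂ can be estimated, and baseline covariates do not change that.

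**3. The plan's own sample size, to fix n for an illustration.** Inputs from section 3.4: 79% v 94%, two-sided 5%, 80% power, 1:1.

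- Kelsey: (1.960 + 0.842)² × 0.865 × 0.135 × 2 / 0.15² = 81.5 per arm (plan: 81).
- Fleiss: 81 (plan: 80); with continuity correction 94 (plan: 93).
- Loss to follow-up: 93 × 1.1 = 102.3, rounded up to 103 per arm, 206 in total, as stated.

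The figures agree to within about one participant per arm. The sample size is not in question, and it rests on viral suppression.

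**4. How small an instrument gap would matter?** The documents give neither a cut-off for the score nor its expected level. Assumptions: score dichotomised; true adherent proportion p equal in both arms, varied from 70% to 90%; SoC read without error; dashboard reads p + b; uncorrected Pearson chi-square, two-sided 5%. The rejection probability is the sum, over all pairs (x, y) with χ² at or above 3.84, of Bin(x; n, p) × Bin(y; n, p + b). With b = 0 it is about 5%. The smallest b on a 0.1-point grid giving at least 10% is:

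| True p | n = 93 per arm | n = 103 per arm |
|---|---|---|
| 70% | 4.3 points | 4.1 points |
| 80% | 3.8 | 3.6 |
| 85% | 3.3 | 3.1 |
| 90% | 2.7 | 2.6 |

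The same sum with the dashboard under-reading (p − b) gives 4.4, 4.0, 3.7 and 3.1 points at n = 93, so the picture is much the same in either direction.

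**5. Do the documents say how large the gap is?** No. Section 2.2 cites a Ugandan study with 89.5% (adults) and 92.8% (children) by electronic monitor against 99–100% by IVR/SMS self-report. The gap runs from 99 − 92.8 = 6.2 to 100 − 89.5 = 10.5 points. It shows that IVR self-report can exceed another instrument. It does not compare IVR with the Care Card, and the figures read as adherence levels rather than proportions of adherent patients, so they are not used above.

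**The case against.** The strongest reply is that viral suppression carries the efficacy question. Section 2.6 uses it as the proxy for adherence, the sample size is built on it, it is measured identically in both arms, and the explicit across-arm comparisons (survival curves, counts of suppressed patients) concern it. Being listed first does not make the score primary. This stands, and it limits the damage: suppression can be interpreted whatever happens to the score. It does not rescue the score itself, which remains a stated outcome serving a specific objective.

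A second reply is that CFLU participants also receive standard of care and so probably have a Care Card; the gap would then be an unspecified extraction, not an irreparable design fault. That is fair, and it is why the repair is cheap. The plan nevertheless assigns the card score to SoC only.

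Third, the chi-square illustration tests something the plan does not specify: arm is not among the listed bivariate covariates, and no cut-off for the score is given. That is correct. The illustration shows sensitivity only and is not the basis of the conclusion.

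Fourth, the point about the logistic legend depends on reading one word literally against the surrounding prose. It is a matter to clarify and does not add to the main finding.

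**Conclusion.** The plan is wrong as written on this point. For the month 6 and 12 adherence score, instrument equals arm, so neither a difference nor the absence of one can be attributed to CFLU. That follows from the outcome definition and the registration rule and needs no numerical assumption. The size and direction of the bias are unknown. Under the assumptions in step 4, an over-reading of roughly 3 to 4 points is enough to double the false-positive rate, with no true effect. The finding does not extend to viral suppression analysed alone, to retention or to stigma.

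**What to change.** Specify one adherence source for both arms at months 6 and 12, chosen before follow-up data are examined.

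- **Option 1 (simplest): Care Card adherence entry, transcribed for all participants.** This needs one added field, because the transcription plan names only regimen and start dates. The cost is at most 206 × 2 = 412 entries, or 103 × 2 = 206 if SoC capture is regarded as already planned. Downsides: the card may be coarser than daily responses, and staff completing it for CFLU participants may have seen dashboard data through the web interface.
- **Option 2: the missed-dose item in Appendix viii.** No new data are needed, but a written rule must turn nine reasons and four frequency options into a score. Reasons can overlap and no count of missed doses is recorded, so the score would be ad hoc. It is also self-report by participants who know their arm.
- **For visits still to come,** the 0–100 rating in Appendix xi could be repeated at months 6 and 12 in both arms, with the same self-report limitation.

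Whichever is chosen, report dashboard and IVR responses only as engagement within the CFLU arm, and state how unanswered calls are counted. Base the between-arm conclusion on viral suppression modelled as its own outcome, and correct the logistic legend so that it is not combined with the adherence score. None of this needs extra visits.
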